6.3 Storage and handling of IMP(s) at site

All IMP aspects of the trial at participating sites are the responsibility of the PI, who may delegate this duty to the local pharmacist or other appropriately trained personnel. The delegation of duties must be recorded on the Staff Signature and Delegation of Tasks.

Storage and handling (e.g., labelling) of the IMP will be completed in accordance with the relevant SPC and summary of drug arrangements. Exenatide requires refrigerated storage (2-8°C). Once removed from the refrigerator, Exenatide needs to stand at room temperature for at least 15 minutes before administration. All patients will be instructed how to operate the pen device and to perform the injections. They will perform their first injection with supervision of the trial team at the end of the baseline visit.

For home visits, dispensing of IMP will be performed by trial pharmacy and transported to the patient in an appropriate cool bag with temperature logger by the clinical trial team. The trial team member will check the temperature logger to ensure the temperature has stayed within the range 2-8°C. If the temperature has fallen out of range the IMP must not be dispensed to the patient and should be returned to the trial pharmacy.

Detailed instructions are contained in the summary of drug arrangements.

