8.1 Pre-treatment Assessments

Screening assessments – Visit 1

Short title: Exenatide once-weekly as a treatment for Multiple System Atrophy Sponsor code: 125591

Participants will attend the research centre for informed consent to the trial. The following trial specific procedures will be carried out after consent to assess the participant's eligibility:

- Demographics recorded
- Medical History recorded
- Family History recorded
- All available brain imaging will be recorded
- Any previous genetic tests recorded e.g. if testing has been performed for Spinocerebellar ataxia or Fragile X tremor/ataxia syndrome
- Previous drug compliance issues recorded
- Physical Examination
- Neurological Examination
- 12-Lead ECG
- Routine bloods (FBC, U&E, LFT, glucose, amylase, HbA1c, PT and APTT)
- Height and weight
- Vital signs
- Serum and urine pregnancy test (for women of child bearing potential)
- MoCA
- BDI-II
- Concomitant Medications

At this visit the investigator will also ensure the patient is asked about speech/swallowing and mobility to assess exclusion criteria number 3. Eligible patients will wear a sensor attached by sticking plaster over their lower back for 1 week. They will bring this back to the trial team at the baseline visit or send to the trial team using a Stamped Addressed Envelope.

Participants will be randomised to either the trial drug or control arm.

Week 0 (Baseline assessments) – Visit 2

Patients will attend the research centre for the following trial procedures:

- Physical Examination (if deemed necessary by trial clinician for clinical purposes)
- Neurological Examination (if deemed necessary by trial clinician for clinical purposes)
- Lumbar puncture for CSF collection
- Serum collection
- Fasting blood tests (glucose, insulin, c-peptide and triglycerides)
- Vital signs
- UMSARS
- COMPASS Select
- MSA-QoL scale
- Timed Motor Tests
- The Unified Dystonia Rating scale
- MoCA
- BDI-II

- Concomitant Medications review
- Adverse Events review

Participants randomised to the trial drug arm will be dispensed the trial medication and receive teaching on its use.

All pre-treatment procedures will be carried out as specified in the schedule of assessments (appendix 1).

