8.2 Randomisation Procedures

All enrolled participants will be entered onto an enrolment log.

Participant randomisation will be undertaken remotely at site using Sealed Envelope, an online service for the randomisation of participants in a clinical trial.

Following participant consent, and confirmation of eligibility (see section 8.1 for pre-treatment assessments) the randomisation procedure described below will be carried out.

Participants will be randomised to receive the trial drug added to their treatment or to continue to receive existing treatment alone. The investigator will enter the patient's initials, gender, date of birth, date of consent, criteria fulfilment and MSA phenotype strata into the Sealed Envelope secure website. A random sequence for study arm allocation will be computer generated by a randomisation service provider (Sealed Envelope.com). Sealed Envelope will provide a unique trial identification code for each recruited participant. Blocking will be used within strata to enable achievement of approximately equal numbers in each group.

Strata 1= Phenotype consistent with MSA-C.

Strata 2= Phenotype consistent with MSA-P

A list of the trial identification codes and treatment allocation will be stored in a secure cabinet with the study team. The randomisation list will be sufficiently long to enable continued randomisation should any patients drop out within the first 9 months. All randomisation procedures will take place during working hours.

Participants are considered to be enrolled into the trial following: consent, pre-treatment assessments (see section 8.1), confirmation of eligibility, completion of the randomisation process, allocation of the participant trial number and treatment by the remote system.

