11.3 Randomisation methods

A random sequence for study arm allocation will be computer generated by a randomisation service provider (SealedEnvelope.com). Sealed Envelope will provide a unique trial identification code for each recruited participant. Stratified randomisation will be performed with strata defined by MSA sub-type. Blocking will be used within strata to enable achievement of equal numbers in each group.

Strata 1 = MSA of parkinsonian sub-type (MSA-P)

Strata 2 = MSA of cerebellar sub-type (MSA-C)

At the baseline visit, the clinical investigator will enter the patient's initials, gender, date of birth, date of consent, criteria fulfilment and MSA sub-type strata into the SealedEnvelope.com secure website which will then allocate the appropriate trial identification code to the patient.

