Appendix 1 - Schedule of assessments

1. Medical History: including MSA history, family history, medication history, previous imaging, previous genetic tests and previous drug compliance issues.
2. Vital signs: blood pressure, respiratory rate, heart rate, temperature, oxygen saturation and weight.
3. Routine blood tests: FBC, U&E, LFT, glucose, amylase, HbA1c, PT and APTT (PT and APTT not done at weeks 24 and 36).
4. Fasting blood tests
 - Baseline visit: glucose, insulin, c-peptide, and triglycerides.
 - Week 24 visit: glucose, insulin, c-peptide.
 - Week 48 visit: glucose, insulin, c-peptide.
5. 5 IMP administration: Participants will be randomly allocated into 2 groups to receive either Exenatide (n[~]=25) or best medical treatment (n[~]=25). Only participants randomised to the Exenatide arm will receive the IMP.
 6. At Week 4 the study nurse will call the participants to provide support and optimise compliance.
 7. At Week 58 the study nurse will call the participants to perform an adverse event check.

8. Randomisation will occur once eligibility has been confirmed prior to Visit 2 to allow Pharmacy team time to prepare IMP for dispensing.
9. * Clinical and Neurological examinations will be performed with deemed relevant/necessary by trial clinician for clinical purposes.
10. Only a serum sample will be collected for research purposes at week 96.

Appendix 2

COVID19 mitigation plans

The objective of this Appendix is to set out a plan detailing the proposed continuation of the Exenatide-MSA trial if a restriction in trial Face to Face visits should occur as a result of a resurgence of COVID19 infections.

CONTINUATION OF IMP DISPENSING FOR EXISTING TRIAL RECRUITS

1. Patient consent required. Each patient will be contacted by the research team, at site. Consent to ship IMP to the patients home to be fully documented in source notes
2. Patient will be assessed via telephone by Chief Investigator (or appropriate delegated trial team member) to decipher whether suitable to dispense IMP. Specific questions to be asked in relation to abdominal pain/ weight/ AEs/ new con-meds etc.

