#### 4.2 Randomisation

Patients will be randomly assigned in a 1:1 ratio to receive the Exenatide together with standard treatment options or to receive the standard treatment options alone. Randomisation will be stratified by MSA phenotype strata using block randomisation to enable achievement of approximately equal numbers in each group. Full details can be found in the randomisation protocol.

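### Protocol section 11.3 and Appendix 1 footnote 8 disagree on when randomisation happens; under footnote 8 the baseline UMSARS covariate is rated after allocation, with no stated rule withholding it

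*Protocol*

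**What the plan says.** Four places in the protocol bear on the timing.

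- Appendix 1, footnote 8: "Randomisation will occur once eligibility has been confirmed prior to Visit 2 to allow Pharmacy team time to prepare IMP for dispensing". Section 8 defines Visit 2 as the baseline visit.
- Section 8.1, in the last line of the Visit 1 text and before the Week 0 heading: "Participants will be randomised to either the trial drug or control arm".
- Section 11.3: "At the baseline visit, the clinical investigator will enter the" patient's details into the randomisation website, which then allocates. The order relative to UMSARS is not given.
- Section 8.2 defines enrolment as following "consent, pre-treatment assessments (see section 8.1), confirmation of eligibility, completion of the randomisation process". Section 8.1 covers both Visit 1 and Visit 2, so this fits either order.

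UMSARS and MSA-QoL first appear in the Week 0 list of section 8.1, and SAP Table 1 also starts them at week 0. MoCA and BDI-II are done at screening as well, so they have an earlier value. Baseline UMSARS is a covariate in the protocol's ANCOVA (section 11.4.2), in the SAP's primary mixed model (section 7.2) and in its single-level sensitivity model (section 7.5).

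On access to the allocation, section 8.2 has the investigator run the randomisation and adds: "A list of the trial identification codes and treatment allocation will be stored in a secure cabinet with the study team". At Week 0, after the assessments, section 8.1 says: "Participants randomised to the trial drug arm will be dispensed the trial medication and receive teaching on its use". Section 6.3 adds: "They will perform their first injection with supervision of the trial team at the end of the baseline visit". SAP section 4.2 refers elsewhere for the rest: "Full details can be found in the randomisation protocol". That document was not available for this review.

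**The concern.** Randomisation cannot be both at Visit 2 and before it. Footnote 8 gives an operational reason, so it reads as intended workflow. If it is followed, the baseline UMSARS is scored after the arm has been assigned. Rating before the first dose separates the score from drug exposure, but not from knowledge of the arm.

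Baseline adjustment assumes a covariate that knowledge of allocation cannot affect. If the two arms are scored differently at baseline for that reason, and only at baseline, the difference passes into the week-48 effect with opposite sign. With a planned baseline-to-final correlation of 0.85, the covariate carries heavy weight. No planned analysis would detect this. The optional blinded video rescoring in section 8.6 covers Part II only. Part I is 12 of the 26 items, or 48 of 104 points (46%).

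**Working it through.** **Inputs.** From protocol section 11.2.1: SD 10.4, correlation 0.85, target difference 5 points, 20 per arm analysed, two-sided 5%. The documents give no size for a rating shift, so s = 0.5, 1 and 2 points are assumed. Here s is the amount by which the exenatide arm is over-scored at baseline relative to control.

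**The plan's own figure.** Residual SD = 10.4 × √(1 − 0.85²) = 5.48. The normal approximation gives n = 2 × (5.48 × (1.96 + 0.84) / 5)² = 18.85, so 19 per arm. With the t distribution, 20 per arm gives 80.2% power, and 40 / 0.8 = 50. The stated 40 and 50 are reproduced.

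**Bias.** Slope = 0.85 × SD_final / SD_baseline = 0.85 with equal SDs, so a baseline-only shift gives bias = −0.85s.

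**Type I error, single-time-point ANCOVA, 20 per arm.** Rejection = P(Z > 1.96 − b/SE) + P(Z < −1.96 − b/SE), with b the bias.

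- Reading A, 10.4 is the cross-sectional SD: SE = 5.48 × √(2/20) = 1.73.
- Reading B, 10.4 is the SD of change, as its place beside the mean decline may suggest: SD = 10.4 / √(2 × 0.15) = 18.99, residual SD 10.00, SE = 3.16.

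| s | Bias | Share of 5 points | Type I, A | Type I, B |
|---|---|---|---|---|
| 0.5 | −0.425 | 8.5% | 5.7% | 5.2% |
| 1 | −0.85 | 17% | 7.8% | 5.8% |
| 2 | −1.70 | 34% | 16.5% | 8.4% |

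A 20,000-run ANCOVA simulation under reading A gave 7.8% at s = 1 and 15.4% at s = 2.

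**SAP mixed model.** Simulated with 20 per arm, complete data, all visits correlated 0.85 and 3,000 runs per case. The slope is again 0.85 and the SE is 1.74 (A) or 3.18 (B). Rejection for s = 0, 0.5, 1 and 2 is 5.4%, 6.2%, 7.9% and 16.9% under A, and 6.0%, 5.6%, 6.1% and 9.4% under B. Simulation error is about 0.4 percentage points (√(0.05 × 0.95 / 3000)), so under B nothing is detectable below s = 2.

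If correlation decays as 0.85^(weeks/48), the baseline correlations are 0.960, 0.922, 0.885 and 0.850. Their mean, 0.904, is the common slope, so bias is about −0.90s. Rejection rates are not used for this case, because the random-intercept SE is too small there even with no shift.

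**If the shift persists.** Let a fraction f of s persist at week 48 in the same direction. Net bias is (f − 0.85)s with the baseline rated after disclosure, and fs with it rated before. The sizes are equal when 0.85 − f = f, so f = 0.425. With full persistence (f = 1) and s = 1, net bias is 0.15 points when rated after disclosure and 1.0 point when rated before.

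**The case against.** The strongest case is that only the wording conflict is firm.

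- **Knowledge at rating is inferred.** Dispensing is listed after the assessments, and the randomisation protocol may already contain a concealment rule. This stands, and it is why the point is called a risk.
- **Randomisation may in fact occur at Visit 2.** SAP Table 1 puts eligibility confirmation at week 0, and section 8.2 has randomisation follow it. That gives section 11.3 some support, but it does not settle the order relative to UMSARS.
- **A screening UMSARS may exist.** The UMSARS rows of the Appendix 1 table show seven marks against six visits listed in the text. However, the columns are displaced in the text available, and MoCA and BDI-II show the same excess of one (eight against seven). The table cannot settle it, and section 8.1 and SAP Table 1 support week 0.
- **The fix could raise net bias.** True if more than 42.5% of a shift persists in the same direction, which is plausible when follow-up is also unblinded. But partial cancellation of unknown size is an accident, not a reason to keep the order.
- **It may be too late.** The SAP model indexes 48 patients, which may mean enrolment had ended. That is inference only, and it would limit the remedy to documentation and checking.

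**Conclusion.** The concern holds as a risk of bias. The passages conflict, and under footnote 8 a covariate of the primary analysis is rated after allocation in an open-label trial, with no rule in the protocol or SAP withholding the allocation. Confidence is medium, because knowledge at rating is inferred and the randomisation protocol was not seen.

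The sizes rest on assumed shifts confined to baseline, equal SDs and a slope of 0.85. They range from slight (half a point, type I error 5.2% to 5.7%) to material (two points, 8.4% to 16.5%), both in the single-time-point analysis. Bias in the unblinded follow-up ratings remains the larger, accepted limitation of this pilot and is untouched by this point. The correction should be made because it is cheap and protects the one rating that can be taken before anyone needs to know the arm.

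**What to change.** Make sections 8.1, 8.2 and 11.3 and Appendix 1 footnote 8 state one order: baseline UMSARS and the other Visit 2 outcome scales are completed and locked before the allocation is disclosed to participant or rater. There are two ways to do this.

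- Randomise at Visit 2 after these scales.
- Randomise earlier, with the allocation released only to pharmacy until the scales are entered.

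Choosing section 11.3 alone is not enough, because it does not place UMSARS before the website entry. If the randomisation protocol already has such a rule, cite it in these places.

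Record the date and time of randomisation and of the baseline UMSARS for every patient. If the screening scores on UMSARS items 1, 2, 7 and 8 used for exclusion criterion 3 were kept, they allow a partial check on four Part I items.

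The cost is protocol wording plus either same-day dispensing or a change in who handles the allocation. Section 6.4 says hospital stock needs no further preparation before dispensing, although labelling, accountability and the summary of drug arrangements (not seen) may still take time. No extra visit or assessor is needed.

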## 1 Administrative information

### 1.1 Trial full title

A Phase IIa, open label, single-site, 48 week randomised controlled trial evaluating the safety and efficacy of Exenatide once-weekly in the treatment of patients with Multiple System Atrophy.

### 1.2 Purpose

This Statistical Analysis Plan describes a protocol-specified analysis of the investigational medicinal product Trial.

### 1.3 Protocol version

This SAP has been written based on information contained in the study protocol version 4.0, dated 14 Sep 2021. Full details of the trial design, population, intervention, comparison and outcome variables may be found in the protocol.

### 1.4 Trial registration

This trial was prospectively registered with ClinicalTrials.gov (NCT04431713).

### 1.5 Authorship

This SAP has been written by [name] and [name] (Lead Statistician), following the guidelines of Gamble *et al* (JAMA 2017. doi:10.1001/jama.2017.18556).

### 1.6 SAP revisions

There have been no revisions. This is version 1.0.

### 3 Introduction

#### 3.1 Background

Multiple System Atrophy (MSA) has a prevalence of 4.4 in 100,000 individuals and there are no effective treatments that can slow down or modify the course of disease progression. There is thus an urgent unmet need for novel treatments that may slow or halt disease progression in MSA. Recent studies have shown encouraging results of using Exenatide in further neurodegenerative diseases. A simple randomised trial was therefore needed to compare use of Exenatide against standard treatment option in MSA. A full description of the trial is contained in the protocol.

#### 3.2 Principle research objectives

To collect pilot data from which to estimate the effectiveness of Exenatide in modifying disease progression of patients with MSA. The primary endpoint will be the difference in total Unified Multiple System Atrophy Rating Scale (UMSARS) score (Parts I and II) at 48 weeks comparing exenatide to best medically treated patients. Secondary measures will include adverse event reports, self-completed questionnaires, and blood test results.

### 4 Study Method

#### 4.1 Trial design

This is a non-commercial, open label trial of a licensed drug designed to primarily provide preliminary efficacy and safety data for the use of Exenatide in MSA. This will be a simple parallel group design and include a 48-week exposure period. Detailed evaluations will take place at Screening, Baseline, 12, 24, 36, 48 and 96 weeks.

#### 4.2 Randomisation

Patients will be randomly assigned in a 1:1 ratio to receive the Exenatide together with standard treatment options or to receive the standard treatment options alone. Randomisation will be stratified by MSA phenotype strata using block randomisation to enable achievement of approximately equal numbers in each group. Full details can be found in the randomisation protocol.

#### 4.3 Sample size

The recent rasagiline for MSA (MSA-Ras) trial evaluated rasagiline versus placebo using the UMSARS total (Parts I and II) as the primary efficacy measure after 48 weeks treatment. Patients in the placebo group declined by mean 7.8 points (SD 10.4 – Werner et al. 2015).

Therefore, on the basis of this previously collected data and with a two-sided 5% significance level, we estimated that a sample size of 40 patients (20 per group) would be required to detect a difference of 5 total UMSARS points between the two groups, assuming a correlation between baseline and final disease severity of 0.85. These calculations were based on a common SD of 10.4, 80% power and an

overall type 1 error rate of 5%. A 5-point difference between groups would be a clinically important effect size. Based on a 20% dropout rate as reported from previous trials, the sample size would be 50 (25 per arm).

## 5 Statistical Principles

### 5.1 Confidence intervals and p-values

All statistical tests and confidence intervals will be 2-sided. Significance will be considered at the 5% level and confidence intervals will be at the 95% level.

### 5.2 Adherence to intervention

Compliance will be assessed by directly questioning patients at each visit, and if applicable carers will also be asked to provide estimates of compliance, along with review of the drug administration diary. Reasons for non-compliance will be sought and addressed as far as possible at each follow up visit.

### 5.3 Analysis Populations

The ‘intention-to-treat’ population will include all randomised patients according to the treatment to which they were randomised to receive. Any patients that have withdrawn from the trial, and withdrawn permission to keep and use their data, will be necessarily excluded. The ‘per-protocol’ population will also exclude any patients randomised to standard treatment who have sourced exenatide outside of the trial.

## 6 Trial Population

### 6.1 Recruitment and retention

A CONSORT diagram will be presented to provide a detailed description of participant numbers at each time point during the trial. In addition, a table summarising the number of patients who have been lost to follow up at each stage of the trial and reasons for loss to follow up (if supplied) will be presented.

### 6.2 Baseline characteristics

The demographic information collected at baseline will be presented in a table summarised separately by study arm. Numerical variables will be summarised using either means and standard deviations or medians and interquartile ranges. Categorical variables will be summarised using numbers and proportions. The number of missing observations will be reported. No statistical tests will be performed to assess baseline differences between study arms.

The following baseline characteristics of patients will be summarised by randomised allocation:

- a) Age
- b) Sex
- c) Ethnicity
- d) Weight
- e) Physical Examination
- f) Neurological Examination
- g) Vital Signs
- h) HOMA index

## 7 Analysis

### 7.1 Outcomes

#### 7.1.1 Primary outcome

The primary outcome is the total Unified Multiple System Atrophy Rating Scale (UMSARS) score (Parts I and II) at 48 weeks.

#### 7.1.2 Secondary outcomes

- Patients with loss of independent ambulation by the end of the study, defined by a score of 4 in UMSARS-I item 7 (walking);
- Multiple System Atrophy health-related Quality of life (MSA-QoL) scale at week 48;
- UMSARS score (Parts III and IV) at week 48;
- Anti-parkinsonian or anti-orthostatic hypotension drugs comparing exenatide at week 48;
- The number of falls at week 48;
- Patients reaching a score of 3 or more on UMSARS-I items 1 (speech), 2 (swallowing), and 8 (falling) at week 48;
- Clinical global impression (CGI) at week 48;
- Montreal Cognitive Assessment (MoCA) scores at week 48;
- Safety of exenatide in MSA based on Adverse event reporting.

